18.5. Appendix E : Protocol deviation code list

1. Screening

- 1.01 Patient did not meet eligibility inclusion criterion
- 1.02 Patient met eligibility exclusion criterion
- 1.03 Patient met intra-operative Exclusion criterion
- 1.04 Date of Informed Consent is after registry enrollment
- 1.05 Informed Consent was improperly obtained
- 1.06 Person obtaining Informed Consent did not sign /date the consent form
- 1.07 Informed Consent process collection was not properly documented
- 1.08 Screening other deviation, specify

2. Adverse Events:

- 2.01 UADE / USADE not reported within 24 hours of the investigator first learning of the event

18.7. APPENDIX G: SF 36 Questionnaire

Your Health and Well-Being

[figure not shown]
This survey asks for your views about your health. This information will help keep track of how you feel and how well you are able to do your usual activities. Thank you for completing this survey!

For each of the following questions, please tick the one box that best describes your answer.

1. In general, would you say your health is:

[figure not shown]

2. Compared to one year ago, how would you rate your health in general now?

3. The following questions are about activities you might do during a typical day.

Does your health now limit you in these activities? If so, how much?

4. Climbing several flights of stairs..... 1..... 2..... 3

5. Climbing one flight of stairs..... 1..... 2..... 3

6. Bending, kneeling, or stooping..... 1..... 2..... 3

7. Walking more than a mile..... 1..... 2..... 3

8. Walking several hundred yards..... 1..... 2..... 3

9. Walking one hundred yards..... 1..... 2..... 3

10. Bathing or dressing yourself..... 1..... 2..... 3

4. During the past 4 weeks, how much of the time have you had any of the following problems with your work or other regular daily activities as a result of your physical health?

All of the time	Most of the time	Some of the time	a little of the time	None of the time
▼	▼	▼	▼	▼

[figure not shown]
11. Cut down on the amount of time you spent on work or other activities..... 1..... 2..... 3..... 4..... 5

12. Accomplished less than you would like..... 1..... 2..... 3..... 4..... 5

13. Were limited in the kind of work or other activities..... 1..... 2..... 3..... 4..... 5

14. Had difficulty performing the work or other activities (for example, it took extra effort)..... 1..... 2..... 3..... 4..... 5

5. During the past 4 weeks, have you had any of the following problems with your work or other regular daily activities as a result of any emotional problems (such as feeling depressed or anxious)?

[figure not shown]
• Cut down on the amount of time you spent on work or other activities 1 2 3 4 5

• Accomplished less than you would like 1 2 3 4 5

• Did work or other activities less carefully than usual 1 2 3 4 5

6. During the past 4 weeks, to what extent has your physical health or emotional problems interfered with your normal social activities with family, friends, neighbours, or groups?

Not at all Slightly Moderately Quite a bit Extremely

[figure not shown]
7. How much bodily pain have you had during the past 4 weeks?

None Very mild Mild Moderate Severe Very severe

8. During the past 4 weeks, how much did pain interfere with your normal work (including both work outside the home and housework)?

Not at all A little bit Moderately Quite a bit Extremely

9. These questions are about how you feel and how things have been with you during the past 4 weeks. For each question, please give the one answer that comes closest to the way you have been feeling. How much of the time during the past 4 weeks...

All of the time	Most of the time	Some of the time	A little of the time	None of the time
				

Did you feel full of pep? 1 2 3 4 5

Have you been a very nervous person? 1 2 3 4 5

Have you felt so down in the dumps that nothing could cheer you up? 1 2 3 4 5

Have you felt calm and peaceful? 1 2 3 4 5

Did you have a lot of energy? 1 2 3 4 5

Have you felt downhearted and blue? 1 2 3 4 5

Did you feel worn out? 1 2 3 4 5

Have you been a happy person? 1 2 3 4 5

Did you feel tired? 1 2 3 4 5

10. During the past 4 weeks, how much of the time has your physical health or emotional problems interfered with your social activities (like visiting friends, relatives, etc.)?

All of the time	Most of the time	Some of the time	A little of the time	None of the time
				
 1	 2	 3	 4	 5

11. How TRUE or FALSE is each of the following statements for you?

	Definitely true	Mostly true	Don't know	Mostly false	Definitely false
• I seem to get ill more easily than other people.....					
• I am as healthy as anybody I know.....					
• I expect my health to get worse.....					
• My health is excellent.....					

Thank you for completing these questions!

18.8. APPENDIX H: Echocardiography guidelines

OBJECTIVES of Echocardiographic Imaging Protocol

- The primary objective of the initial echo-Doppler examination is to establish baseline cardiac anatomy and function with an emphasis on the aortic valve, aortic root and left ventricular size and function.
- The primary goals of the follow-up post-implantation studies are to reassess the aortic valve prosthesis (structure and function) and to determine the impact of the implantation on the parameters evaluated.
- Complete Echo-Doppler examinations are required at the time points specified in the table above.
- Two-dimensional ultrasound imaging system with pulsed, continuous wave and colour Doppler capability, and permanent recording capabilities are required.
- The only accepted storage format is DICOM standard digital.
You should have transducers with both fundamental and harmonic capability with frequency ranges that are suitable for most adult subjects (approximately 2 to 7 mHz).

EXAMINATION PREPARATION, POSITIONING, AND GENERAL PROCEDURES

- A qualified physician or sonographer must perform all ultrasound exams. If possible, participating sites should attempt to utilize the same person as well as the same machine for image acquisition throughout the trial.
- Prior to starting the registry, the physician/sonographer should provide the patient with an overview of the registry (duration, general procedure etc).
- Patients will typically be studied while they are in the left lateral decubitus position although occasionally the best images will be obtained with the patient supine.
- EKG leads will be applied and the EKG control setting of the machine optimized to ensure a high quality EKG with adequate amplitude QRS complex for reliable digital capture (lead II equivalent preferred).
- Enter the patient ID as specified on the case report form. Please measure and note the blood pressure on the patient ID screen or as an annotation on one or more images.
- All views will be acquired with 2 captures OF EACH VIEW as follows:
 - Sinus rhythm (up to 90 bpm): 3 beat capture
 - Sinus rhythm (> 90 bpm): 5 beat capture
 - Frequent atrial or ventricular ectopy: 3 second capture
 - Atrial fibrillation or flutter, paced rhythm: 5 second capture
- It is essential that the view be optimized and stabilized before recording. Images are typically acquired during quiet respiration. Breath-holding during recording is not

[figure not shown]
required unless necessary to ensure a stable high quality image.

- The spatial resolution of the images should be optimized using the highest frequencies capable of providing adequate penetration. For each view, the gain and compression and focus should be optimized so that the best echocardiographic image of the endocardial borders is obtained.
- Use echo contrast if available for images with suboptimal endocardial definition.
- The sweep speed for all spectral Doppler and M-mode recordings should be 100 mm/sec. NOTE: at least 3 consecutive sinus beats and at least 5 consecutive "irregular rhythm" beats must be captured, so adjust the number of captures accordingly.
- As defined in the ASE Guidelines for the Quantification of Native Valve Regurgitation, Nyquist settings for color Doppler assessment of the cardiac valves should be 50-60 cm/sec.
- Your performance of measurements is optional. We encourage you to perform measurements as needed for clinical feedback to treating physicians. If you do perform on-line measurements, please do not obscure the flow profiles of subsequent beats. We suggest storing BOTH measured and unmeasured Doppler spectra and images.

EXAMINATION SEQUENCE

I. Parasternal Long Axis of LV, LVOT and aortic valve

- 2D (Image A below)
- Colour Doppler of MR
- Colour Doppler of LVOT and aortic valve for aortic insufficiency
- Magnified views of LVOT and aortic valve – to identify the true LVOT dimension, AV annulus and stent diameter. (Image B below)
- High Parasternal View to see ascending aorta
- Off-axis views to search for aortic paravalvular leak

A.

B.

[figure not shown]
CONFIDENTIAL AND PROPRIETARY DATA: This document and the information contained herein may not be reproduced, used, or disclosed without written permission from Edwards Lifesciences SA

II. Parasternal Short axis at LV level

- 2D should be obtained at 3 levels: apex, mid-papillary muscle and base.
- Colour Doppler of MR from the basal view is also required.

[figure not shown]
III. Parasternal Short axis at aortic valve level

- 2D
- Colour Doppler of aortic valve including sewing ring of prosthesis to search for paravalvular leak
- Colour Doppler of TR is optional in this view

IV. Apical 4 chamber

- 2D optimizing LV endocardial borders: Need to see all aspects of the lateral wall, septum, and apex
- Show a loop with decreased depth such that LV occupies most of the imaging sector ensuring all walls are visualized
- Colour Doppler of MR showing entire left atrium (to allow jet dimension/LA measurement).
- If there is more than mild MR, provide components for PISA calculation
 - CW of MR jet
 - Zoomed PISA display (baseline shift down to optimize hemispherical PISA shell)
 - If possible, provide split screen (colour suppress) images (i.e. one side with colour, one without)
- Colour Doppler of TR with CW

[figure not shown]

A. B.

* Image A shows the traditional 4 chamber while image B shows the 4 chamber with decreased depth.

V. Apical 2 chamber

- 2D optimizing LV endocardial borders : Need to see all aspects of the anterior wall, inferior wall, and apex
- Show a loop with decreased depth such that LV occupies most of the imaging sector ensuring all walls are visualized
- Colour Doppler of MR

A. B.

* Image A shows the traditional 2 chamber while image B shows the 2 chamber with decreased depth.

VI. Apical 5 chamber view

[figure not shown]
- Pulse wave Doppler of LVOT (to avoid the region of flow acceleration - sample volume should be positioned at valve level and then moved apically until valve noise or "clicks" are no longer detected and then recorded for the baseline registry).
- For post-implantation studies, it is imperative that the sample volume be placed proximal to the valve frame AND at a second position within the valve frame but

proximal to the valve cusps. Studies in which there are no clips with the sample volume proximal to the valve frame will be considered INADEQUATE.

- Note: record a full screen 2D image showing the pulsed wave sample position (either as moving image or still frame) as well as the Pulse Wave Spectral Doppler for each position. It is very difficult to establish the sample volume position from the small image that is available when image and spectral display are provided simultaneously.
- Colour Doppler of LVOT and aortic valve for AI (use off axis views to ensure that all AI jets are demonstrated).
- Continuous wave Doppler through the aortic valve.

VII. Apical long axis view (also known as 3 chamber view)

- 2D optimizing LV endocardial borders
- Show a loop with decreased depth such that LV occupies most of the imaging sector ensuring all walls are visualized
- Continuous Wave Doppler through the aortic valve
- Colour Doppler of MR
- Colour Doppler of LVOT and aortic valve for AI (use off axis views to ensure that all AI jets are demonstrated)
- Pulse Wave Doppler just apical to the valve frame as specified in apical 5 chamber view
- Note: record a full screen 2D image showing the pulsed wave sample position (either as moving image or still frame) as well as the Pulse Wave Spectral Doppler for each position

VIII. Right Parasternal view

- Continuous Wave Doppler through the aortic valve (Note: this view is particularly useful if you notice an anteriorly-directed transaortic jet from parasternal views)

IX. Suprasternal Notch view

- Pulsed Doppler of the descending thoracic aorta from the suprasternal notch should be obtained to assess for reversal of flow if significant (moderate or greater) aortic insufficiency is present (Note: sample volume is placed in the descending thoracic aorta below the take off of the subclavian artery).
- Continuous wave Doppler interrogation of the transaortic valvular flow should also be obtained using the pedoff transducer.

Specific Comments on Imaging Planes

A. Parasternal long axis view is recorded with the transducer in the third or fourth intercostal space immediately to the left of the sternum. The transducer should be angled so that the aortic valve, mitral valve and left ventricle are in their long axis.

IMAGING TIP 1: PARASTERNAL LONG AXIS VIEW

It is important that the parasternal long axis view displays the true long axis of the ventricle with the left ventricle lying horizontally on the image. If it is impossible to obtain a single view which optimally displays the long axis of the aortic valve and aortic root as well as the long axis of the left ventricle, record 2 separate views. It is unacceptable to record an-off-axis view in which the apex "points up" on the screen. If this type of image is obtained try moving the transducer up an intercostal space or 2 or having the patient take a breath in. Sometimes having the patient move to a more lateral decubitus position will help as well.

IMAGING TIP 2: PARASTERNAL LONG AXIS VIEW

Measurement of the left ventricular outflow tract and aortic annulus is a key component of the registry. In pre-device imaging, it is important to note that the largest annulus may not be in a plane with valve opening centered in the aorta.

B. Parasternal short axis view is obtained by angling the probe 90° with respect to the parasternal long axis of the LV. The goal of this view is to obtain information about the aortic valve as well as the LV.

IMAGING TIP 3: PARASTERNAL SHORT AXIS VIEW

This is an essential view post-op to completely assess aortic regurgitation. This may be the only view in which prosthetic valve medial or lateral aortic regurgitant jets are imaged. Imaging at the level of as well as just below the leaflets may allow you to better image these jets.

C. Apical four-chamber view provides considerable information including the relative sizes of the right and the left ventricles and the regional function of the LV. The four chamber view is defined as a view which maximizes the LV long axis and the tricuspid and mitral annular dimensions. In this view, the full excursion of the mitral and tricuspid valves should be seen. The complete endocardial border of the LV will be traced for chamber volume assessment (method of discs) so all aspects including the apex should be visualized. In the apical four chamber view, colour Doppler of mitral and tricuspid regurgitation should be recorded. The four chamber view should visualize the lateral, septal and apical walls.

D. Apical two-chamber view should be obtained for the goal of assessment of LV size and function. The complete endocardial border of the LV will be traced for chamber volume assessment (method of discs) so all aspects including the apex should be visualized. The degree of MR by colour Doppler will also be assessed. The two chamber view should visualize the anterior, inferior and apical walls.

IMAGING TIP 4: APICAL 4 and 2 CHAMBER VIEWS

Because we will measure volumes from the apical views as an important end-point of the registry, please try to avoid apical foreshortening. If the view appears to be foreshortened, please bring the transducer down one intercostals space and have the patient take a breath in (particularly for the apical two-chamber view). Sometimes this will bring out a better (not foreshortened) view.

E. Apical 5 chamber and 3 chamber views are obtained to provide detailed information about the aortic valve colour, spectral and continuous wave Doppler.

IMAGING TIP 5: APICAL 5 and 3 CHAMBER VIEWS

Both these views are essential in imaging post-device aortic regurgitant jets. Because we will be measuring jet vena contracta and jet length, a Res/Zoom view which includes imaging of the entire jet would be helpful. In addition, the 3Ch view may be used in the biplane Simpson's calculation of LV volume when the 2Ch view is inadequate thus careful attention to endocardial definition is important.

XI. Abbreviations

2D – Two-dimensional	LV – Left Ventricle
AI – Aortic Insufficiency	LVED – Left ventricular end diastolic volume
AVA – Aortic valve area	LVEF – Left ventricular ejection fraction
AR – Aortic Regurgitation	LVES – Left ventricular end systolic volume
AV – Aortic Valve	LVOT – Left ventricular outflow tract
BSA – Body Surface Area	MR – Mitral Regurgitation
ED – End diastole	MV – Mitral Valve
CO – Cardiac Output	PI – Performance Index
CSA – Cross sectional area	PW – Pulse wave
EF – Ejection fraction	SV – Stroke Volume
ES – End systole	TR – Tricuspid Regurgitation
HR – Heart rate	TVI or VTI – Time Velocity Integral
LA – Left atrium

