9.7. Hospital Discharge

The clinical evaluation and data requirements for the registry subjects at the time of hospital discharge:

- Fitness for hospital discharge

- **Length of stay:** Total length of stay in hospital and duration in ICU
- **Disposition at hospital discharge:** home, rehabilitation unit
- **Adverse Events:** Post-operative procedure or cardiac related events that resulted in medical or surgical intervention; all other serious adverse events per investigators decision using the available adverse event code list will also be collected
- **Medical examination:** NYHA classification, weight
- **ECG 12 lead**
- **Echocardiography data will be collected (if available) and CD will be sent to CoreLab**
- **Anticoagulation therapy**
- **Coagulation profile, if patient is being treated with a coumadin derivation medication (INR and PT)**
- **Blood Studies: RBC, WBC, HGB, HCT, Reticulocytes, Platelet counts, Serum Creatinine (if available per standard of care)**

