9.8. Follow-up Visits Registry Procedures

9.8.1. FOLLOW-UP VISIT WINDOWS

Post-procedure clinical evaluation will be performed on all enrolled subjects at 30-days and 6-months post-implant date. Follow-up at 30 days- will be conducted by phone. All follow-up data will be documented on the CRF.

Patient assessments will be done according to the sites standard of care.

It is important that the follow-up visit schedule is maintained as closely as possible for all subjects. Edward's recognizes that subjects may not be able to return for all scheduled visits at precisely the date required, and therefore, an acceptable window of time for the 30 day follow-up period is described in Table 1. Registry visits should be scheduled as close to the earliest portion of the window for the follow-up period so that cancellations and visit rescheduling can still be conducted within the required time period.

TABLE 1. SCHEDULED FOLLOW-UP VISIT DAYS AND APPLICABLE VISIT WINDOWS

Visit	Visit Window days	Timing from Implant (Day 0)
Screening		Day -30 to Day -1
Discharge		Post-op - Day of Discharge
POD 30	+/- 7	Day 23 to Day 37
POD 180 (if applicable)	+/- 45	Day 135 to Day 225

Protocol required registry follow-up not performed will be considered a missed visit.

9.8.2. 30 DAYS FOLLOW-UP VISIT: REQUIRED PROCEDURES AND EVALUATIONS

The 30 day follow-up visit shall be performed by phone. The clinical evaluation and data requirements for the registry subjects at POD 30:

- Adverse Events: Post-operative procedure or cardiac related events that resulted in medical or surgical intervention; all other serious adverse events per investigators decision using the available adverse event code list will also be collected.
- NYHA classification

9.8.3. 180 DAYS (6 MONTHS) FOLLOW-UP VISIT: REQUIRED PROCEDURES AND EVALUATIONS

The 6 month follow-up visit shall be performed at the investigational site, if applicable. The clinical evaluation and data requirements for the registry subjects at POD 180:

- Adverse Events: Post-operative procedure or cardiac related events that resulted in medical or surgical intervention all other serious adverse events per investigators decision using the available adverse event code list will also be collected.
- Medical examination: HR, BP, NYHA classification, weight
- ECG 12 lead
- Echocardiography data will be collected (if available and CD will be sent to CoreLab)
- Anticoagulation therapy
- Coagulation profile: INR and PT

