New or worsening implant related conduction disturbance requiring a permanent pacemaker implantation	Any new or worsened implant-related cardiac conduction disturbance requiring implantation of permanent pacemaker.
Valve thrombosis	Any thrombus attached to or near an implanted valve that occludes part of the blood flow path, interferes with valve function, or is sufficiently large to warrant treatment. Valve thrombus found at autopsy in a patient whose cause of death was not valve related or found at operation for an unrelated indication should also be reported as valve thrombosis.
Deep sternal wound infection	Deep sternal wound infection involving muscle, bone, and/or mediastinal contents confirmed by positive tissue cultures and requiring intervention (wound opening and excision of tissue ; or re-exploration for washout and treatment) and systemic antibiotics.
Structural Valve Deterioration	Structural valve deterioration includes dysfunction or deterioration involving the operated valve (exclusive of infection or thrombosis), as determined by re-operation, autopsy, or clinical investigation. Clinical investigation should include periodic echocardiographic surveillance. Substantially increased regurgitation or stenosis of the operated valve over time should be reported with quantitative or semi-quantitative methods. The term structural valve deterioration refers to changes intrinsic to the valve, such as wear, fracture, poppet escape, calcification, leaflet tear, stent creep, and suture line disruption of components of a prosthetic valve; it also refers to new chordal rupture, leaflet disruption, or leaflet retraction of a repaired valve.
Non Structural Valve Deterioration	Any abnormality not intrinsic to the valve (do not directly involve valve components) itself that results in stenosis or regurgitation of the operated valve or hemolysis (excludes thrombosis and infection). Examples include: Entrapment by pannus, tissue, or suture, paravalvular leak, inappropriate sizing, inappropriate positioning, Regurgitation as a result of technical error, STJ dilation, dilation of the valve annulus, obstruction of the coronary ostia by the registry valve.

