12.2.4. HEMODYNAMIC PERFORMANCE

The following parameters will be summarized (mean, median, standard deviation and interquartile range) at baseline, Discharge and 6 month Follow up visits for all subjects in the study valve population: mean gradient, peak gradient, effective orifice area (EOA), EOA index, performance index, cardiac output, cardiac index, valvular regurgitation (including paravalvular leak), end systolic and end diastolic left ventricular volumes. Valvular regurgitation will be summarized by the number and percentage of subjects in each level of regurgitation. An analysis stratifying by valve size will also be performed.

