12.3. SAFETY DATA

- All cause mortality
 - Study valve-related mortality
- Thromboembolism (Stroke, TIA, and Non cerebral embolism)
- Valve Thrombosis
- Major Bleeding event

- Endocarditis (study valve)
- Structural valve deterioration
- Non Structural valve deterioration
 - Paravalvular Leak minor
 - Paravalvular Leak major
 - Other non SVD
- Hemolysis
- Reoperation
 - Trial valve reoperation
- Study valve explants
- Implant-related new or worsened cardiac conduction disturbance requiring permanent pacemaker implant
- Renal Failure
- Respiratory Failure
- Deep Sternal Wound infection

Early adverse events within 30 days of procedure will be reported as the number of events divided by the number of enrolled subjects. Linearized rates will be used to summarize adverse events for the late (>30 days) post-operative period. The linearized rates will be calculated as the number of late events divided by the total number of late-subject years.

Percentages for the early events and linearized rates for the late events also will be calculated for all other complications observed in the trial.

Actuarial rates based on the method of Kaplan - Meier will be calculated for each of the safety endpoints at thirty days and six months; the number of subjects at risk for death will be reported at each of these intervals.

On top of Implant-related new or worsened cardiac conduction disturbance requiring permanent pacemaker, the counts and percentage of subjects who experience new or worsening cardiac rhythm or conduction disturbances will be calculated at each follow-up visit. The identification of “new and worsening” cardiac rhythm or conduction disturbance will be based on a comparison to the previous visit.

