18.1. APPENDIX A: Table of procedures and flowchart

Time Periods and Assessments	Preoperative	Operative	Discharge	30 Days (Phone)	6 Months (180 days)
Informed Consent	X				
Medical History Aortic Valve Etiology and diagnosis	X				
Inclusion Criteria / General Exclusion Criteria	X				
Medical Examination	X		X		X
Height	X				
Weight	X		X		X
Heart rate and Blood Pressure	X		X		X
NYHA	X		X	X	X
Demographics (DOB& gender)	X				
LVEF	X				
Logistic Euroscore I and II	X				
Pregnancy test (If applicable) ¹	X				
Health care utilization (Length of stay ICU and war0064)			X		

Time Periods and Assessments	Preoperative	Operative	Discharge	30 Days (Phone)	6 Months (180 days)
Implant Procedural Data and timing		X			
Intra-operative Exclusion criteria evaluation		X			
12 Lead Electrocardiogram (EKG)²	X		X		X
Transthoracic Echocardiography and Doppler	X ³		X ⁴		X ⁴
Current Anticoagulation Therapy	X		X		X
Coagulation profile: INR and PT⁵	X		X		X
Blood Studies RBC, WBC, HGB, HCT, Reticulocytes, Platelet counts, Serum Creatinine	X		X		X
Fitness for hospital discharge			X		
Quality of Life (QoL): EQ-5D SF-36	X				X
Adverse Events		X	X	X	X

1 - Pregnancy test is required for female subjects who are not post-menopausal or surgically sterile (urine)

2 - For EKG machine generated reports the Investigator must verify that the cardiac rhythm is correct and sign and date the final EKG report

3 - If available Pre-op echocardiography within 3 months of planned implant date and including echocardiographic data in the format required per the echocardiography guidelines

4 - If available echocardiography data will be collected

5 - Required only if patient is being treated with a coumadin derivation medication

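### Section 12.3 counts subjects without a readable echo as free of silent paravalvular leak, and the documents disagree on whether the echo is required

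*Combined protocol and SAP*

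**What the plan says.** **Status of the echo.** Appendix H (echocardiography guidelines) says: "Complete Echo-Doppler examinations are required at the time points specified in the table above". For the discharge visit, 9.7 says: "Echocardiography data will be collected (if available) and CD will be sent to CoreLab". For the six-month visit, 9.8.3 says: "Echocardiography data will be collected (if available and CD will be sent to CoreLab". In Appendix A the discharge and six-month echoes carry footnote 4, "If available echocardiography data will be collected", and the pre-operative echo carries footnote 3, "If available Pre-op echocardiography within 3 months of planned implant date". Section 7.2 puts the same condition on the hemodynamic endpoint. The 30-day contact (9.8.2) is by telephone, so discharge is the only scheduled echo in the early period.

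**Leak as a safety event.** Sections 7.4 and 12.3 list minor and major paravalvular leak among the safety endpoints. Under Table 2 in 11.2, a grade of at least 3+ is enough for major leak, even without symptoms or intervention. Leak leading to intervention or death, or of that grade at autopsy, also qualifies. Minor leak has no entry in Table 2. On rates, 12.3 says: "Early adverse events within 30 days of procedure will be reported as the number of events divided by the number of enrolled subjects". Late events are divided by all late follow-up in subject-years, and Kaplan-Meier rates are planned as well.

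**Leak as a hemodynamic reading.** Section 12.2.4 includes paravalvular leak within regurgitation: "Valvular regurgitation will be summarized by the number and percentage of subjects in each level of regurgitation". Section 12.4 limits effectiveness summaries to subjects with data and rules out imputation. No such rule is given for safety endpoints.

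**The concern.** A safety rate needs a denominator of people in whom the event could have been seen. A leak that causes trouble declares itself through reoperation, death or autopsy, and can fairly be counted over everyone. A silent leak is seen only if someone images the valve. Where imaging follows local practice, a subject who was never imaged is unknown for silent leak, but 12.3 treats that subject as a non-event.

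Section 4.1 lists leak from insufficient frame expansion among risks that could be unique to this valve system, and 2.2 says the data will support publications and marketing information. When silent leaks go unimaged, the error in the all-subject rate favours the device. The plan does not call for the number imaged to be reported, so a reader could not judge its extent.

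**Working it through.** **Plan's own figures.** The documents give no expected leak rate and no expected share of subjects imaged, so there is nothing on this point to reproduce. The one design figure, power above 90% for cross clamp time in 12.5, reproduces (above 99.9% with 300 against 479 subjects, a 15-minute difference, SD 16.0, two-sided 5%). It does not bear on leak.

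**Inputs.** N = 300 (12.5), taken as the enrolled number. Leak rates and imaging shares are assumed. Every leak considered here is detectable only by echo, and every echo-detected leak is assumed to be entered as a 12.3 event.

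**Formulas.** Let p be the true rate of silent leak, a the share of subjects with leak who are imaged, and f the share of all subjects imaged.

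- All-subject rate, as in 12.3 for early events: p × a
- Imaged-only rate: p × a / f

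**Case 1: imaging unrelated to leak (a = f).** The imaged-only rate equals p and the all-subject rate is p × f. For p = 5% and f = 70%: 210 imaged, 0.05 × 210 = 10.5 expected leaks, 10.5/300 = 3.5%. The all-subject rates are:

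| Leak rate among imaged | 100% imaged | 90% | 70% | 50% |
|---|---|---|---|---|
| 2% | 2.0% | 1.8% | 1.4% | 1.0% |
| 5% | 5.0% | 4.5% | 3.5% | 2.5% |
| 10% | 10.0% | 9.0% | 7.0% | 5.0% |

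**Case 2: imaging favours subjects with leak.** Take p = 10% (30 of 300), with 27 of the 30 with leak and 153 of the 270 without leak imaged. Then 27 + 153 = 180 are imaged, so a = 27/30 = 90% and f = 180/300 = 60%.

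- All-subject rate: 27/300 = 9.0%, 1 point below the truth
- Imaged-only rate: 27/180 = 15.0%, 5 points above the truth

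The all-subject rate cannot exceed p in this set-up, because a is at most 1. The imaged-only rate exceeds p whenever a is larger than f. Neither is safe alone.

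**Late period.** The same mechanism applies to the linearized rate: a subject with no readable six-month echo adds late follow-up time but can add no silent leak.

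**Cohort.** Section 12.1.2 bases safety summaries on the per protocol cohort, while 12.3 divides early events by enrolled subjects. Enrolment under 9.4 precedes surgery, so enrolled subjects can include intra-operative screen failures and people who leave the operating room without the registry valve. Counting them lowers the leak rate further.

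**The case against.** **The wording conflict may be thin.** No table is visible in Appendix H. If the phrase points to Appendix A, the footnotes there already carry the availability condition. Appendix H is also a guideline on image acquisition and could mean that any echo done must be complete. The rest of the protocol consistently describes assessment by local standard of care. This has force, but a site cannot tell which reading applies. The denominator problem remains even if conditional imaging is intended.

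**A reader might infer that one set of core-lab readings will yield two conflicting leak percentages.** The documents do not establish that. The 12.3 events are adverse events reported at the investigator's discretion (11.1) and adjudicated by the events committee. Section 13.2 says only that the committee reviews core-lab data as appropriate. No passage turns a core-lab grade into a 12.3 event, and 12.2.4 tabulates regurgitation by level without specifying a separate leak percentage. Adverse event collection in 9.7 and 9.8 centres on events needing intervention and on serious events, so a minor leak seen on echo might never reach 12.3. This leaves the link between grades and events unstated, which is itself a gap to close.

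**A reader might also want to replace the 12.3 denominator with imaged subjects.** Case 2 shows why not: 15.0% is further from the true 10% than 9.0% is.

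**Nor should structural valve deterioration be limited to subjects with two post-operative echoes.** Table 2 says "Clinical investigation should include periodic echocardiographic surveillance", but it also accepts findings at re-operation or autopsy. Such a limit could remove subjects who die or are explanted before six months.

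**Importance.** Leak is one item in a descriptive safety list with no hypothesis attached. That is correct and bounds the seriousness.

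**Conclusion.** The point holds in limited form. The echo passages conflict on their face and must be reconciled. As written, 12.3 counts a silent leak in an unimaged subject as no leak, so the rate is biased low to the extent that silent leaks go unimaged. Where imaging is unrelated to leak, the relative shortfall equals the share not imaged: 5.0% becomes 4.5%, 3.5% or 2.5% at 90%, 70% or 50% imaged.

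These sizes rest on assumed leak rates and imaging shares, and on echo-detected leaks being entered as 12.3 events. With complete, readable imaging the gap is zero. Leak that surfaces through intervention, death or autopsy is outside the calculation. Reading 12.4 as governing 12.2.4 is natural but not spelled out, and the conclusion does not depend on it.

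**What to change.** - Reconcile Appendix H with 7.2, 9.7, 9.8.3 and Appendix A so that one statement on echo applies, and identify the table Appendix H refers to.
- State in 12.3 whether and how core-lab grades feed the leak endpoint, and define minor leak.
- For echo-detected leak, report the rate over subjects with at least one core-lab-readable post-operative echo in the period beside the all-subject rate. Present neither alone, and state the direction of bias for each.
- Keep leak leading to intervention or death, or found at autopsy, over all subjects.
- Report the number imaged and the number readable at each visit. Compare baseline characteristics and discharge NYHA class between imaged and unimaged subjects.
- Settle the all-subject denominator, choosing between the cohort in 12.1.2 and that in 12.3.
- Leave structural valve deterioration without a two-echo denominator.

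**Cost.** Wording changes and one extra table; the reporting changes need no additional echo. The downside is a second leak rate that is likely to look less favourable, rests on fewer subjects and is open to selective-imaging bias. The primary endpoint and its power are untouched.
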